Patients in this arm will receive an intensive treatment delivered mostly in group format, the Bergen 4-day treatment (B4DT) [6]. The group sizes will be 3-6 participants with a 1:1 patient to therapist ratio. In the week leading up to the intensive part of the treatment, participants will have two scheduled phone/video calls with a therapist to assess readiness and encourage participants to prepare relevant exposure tasks. Day 1 of the intensive treatment includes psychoeducation about the rationale for exposure with response prevention (ERP), and deciding on exposure tasks. Days 2 and 3 focus on individually tailored and therapist-assisted ERP in as many relevant settings as possible (up to 7 hours of ERP per day). In the evenings, patients should continue with self-guided ERP and may receive therapist support via text messages or phone calls on demand. In the afternoon of day 3, patients can invite relatives and friends to a psychoeducation session. Day 4 of the intensive treatment focuses on treatment summary and relapse prevention, as well as planning self-guided ERP for the upcoming 3 weeks. After 14 weeks, participants have individual follow-up sessions at the clinic where they summarize their experiences after completing treatment. There is no ERP during this session.

All groups will be led by a therapist with expertise in B4DT. All therapists will have participated in the Norwegian OCD-training program [12] or have documented equivalent training. Prior to participation, all therapists will have participated in at least two B4DT groups.

Individual CBT

Patients will receive 16 90-minute sessions of individual CBT for OCD with an emphasis on ERP, delivered over a time period of 14 weeks according to a validated protocol [10]. Sessions will be held twice weekly at a specialist clinic during the first 2 weeks and once a week for the remaining 12 weeks. Sessions 1-2 contain psychoeducation about OCD and CBT, goal setting, and planning of ERP exercises. Sessions 3-14 include therapist-guided ERP (at the clinic, in the patients' homes or elsewhere as needed) with planned self-practice ERP between sessions. Sessions 15-16 contain a summary of the treatment and lessons learned, as well as relapse prevention and planning of continued self-practice ERP.

Therapist competence and adherence

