Therapists in both arms will be licensed clinical psychologists or psychologists under supervision employed at the two specialist OCD clinics. All sessions in both treatments will be audiotaped for the purpose of rating competence and adherence. Such ratings will be conducted on 20% of audiotaped sessions (randomly selected) by two independent psychologists not otherwise involved in the study specialized in B4DT, and two independent psychologists specialized in individual CBT treatment for OCD. Adherence to protocol in the B4DT arm will be checked using a treatment checklist, and therapist adherence in the individual CBT arm will be checked using the session checklist in the treatment manual. Therapist competence in both treatment arms will be rated using the Cognitive Therapist Scale-Revised (CTS-R) [22].

Sample size calculation

A power calculation has been conducted in order to determine the number of participants needed to test the primary hypothesis; that B4DT will be non-inferior compared to gold standard CBT at the pre-specified margin of 4 points on the Y-BOCS. Clinical outcome data from a recent randomized controlled trial (individual CBT) and regular clinical practice (B4DT) were obtained to simulate study data. The following parameters were used: A pre-treatment mean of 22.6 (SD = 3.78) for both arms, and a post-treatment mean of 12.9 (SD = 4.07) for the gold standard CBT arm. Statistical power was then assessed by simulating 10000 datasets assuming different true group differences. An ANCOVA was then conducted on each dataset to test for between-group differences at post-treatment accounting for pre-treatment scores. With 60 participants per arm, no difference in efficacy between the treatments, and 10% missing values,

this test has >95% power to demonstrate non-inferiority. Details on this calculation, including analysis code, is provided in the online pre-registration (<https://osf.io/w5bfp/>).

Measurements

Table 2 lists clinician-rated and self-rated assessments at the different time points.

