If a participant expresses suicidal ideation during treatment or at subsequent assessments, assessors will initiate a structured suicide risk assessment in accordance with routines at the clinic. If there is an urgent need for psychiatric care, a trial psychiatrist will contact participants to schedule an appointment as soon as possible. Serious adverse events (e.g., urgent psychiatric care or discontinued treatment due to a worsening of psychiatric symptoms) will be described in detail on a case-by-case basis.

Statistical analysis

All analysis scripts have been uploaded to a public repository with the analysis strategies described in detail using simulated data (<https://osf.io/w5bfp/>).

Primary outcome

Y-BOCS

The primary non-inferiority hypothesis on the clinician-rated Y-BOCS will be evaluated using ANCOVA of group differences at post-treatment with pre-treatment score as covariate. It will be based on participants that have received at least 50% of the treatment (i.e., attended at least 8 sessions of individual CBT or 1.5 days of B4DT) and completed the post treatment assessment 14 weeks after treatment start. This per protocol approach is chosen to avoid potential problems related to study design that can bias the results towards the alternative hypothesis of non-inferiority (the opposite is true in superiority trials). No data imputation will be conducted at this stage. A 95% confidence interval will be used to model the gold standard CBT-B4DT effect. Non-inferiority will be considered supported if the upper bound is less than 4 (the non-inferiority margin) and superiority will be considered supported if the upper bound is less than 0. This testing procedure has the Type I error rate controlled at the 2.5% level for both comparisons.

For sensitivity assessment, the same ANCOVA model will be used again but with an intention to treat approach. Missing data will then be estimated using maximum likelihood after which the models are refitted. The aim of these steps is to address the potential influence of non-random missing data in the primary per protocol analysis.

Non-inferiority margin

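### B4DT is given in groups of 3-6, but the described primary ANCOVA has no group or therapist term, so the 2.5% error claim fails if correlation within groups or therapists is net positive

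*Combined protocol and SAP*

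**What the plan says.** The B4DT part of Interventions states: "Patients in this arm will receive an intensive treatment delivered mostly in group format". It adds "The group sizes will be 3-6 participants with a 1:1 patient to therapist ratio" and "All groups will be led by a therapist with expertise in B4DT". It also says of the middle of the programme: "Days 2 and 3 focus on individually tailored and therapist-assisted ERP in as many relevant settings as possible". Sixty patients therefore form between 60/6 = 10 and 60/3 = 20 groups. The comparator is individual CBT. On staffing, Therapist competence and adherence says: "Therapists in both arms will be licensed clinical psychologists or psychologists under supervision employed at the two specialist OCD clinics". The number of therapists and their caseloads are not given.

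Under Statistical analysis, Primary outcome, the non-inferiority hypothesis "will be evaluated using ANCOVA of group differences at post-treatment with pre-treatment score as covariate". The intention-to-treat sensitivity analysis refits this model. The section then says, with no condition attached, that type I error is controlled at 2.5% for the non-inferiority and the superiority comparison.

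The Sample size calculation uses the same kind of model: "An ANCOVA was then conducted on each dataset to test for between-group differences at post-treatment accounting for pre-treatment scores". With 60 per arm, no true difference and 10% missing, "this test has >95% power to demonstrate non-inferiority".

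No section mentions a therapy-group or therapist effect, an ICC, a mixed model, cluster-robust errors or a design effect. The plan points to analysis code in a public repository. That code could not be seen, so this point concerns the text only.

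**The concern.** The design is partially nested: B4DT patients share a group and a leader, while CBT patients share at most a therapist. An ordinary ANCOVA treats all patients as independent. If patients in the same group, or with the same therapist, tend to do similarly well or badly, the true standard error of the treatment difference is larger than the one the model reports. The 95% interval is then too short and its upper bound too low. That makes a false finding of non-inferiority, and then of superiority, more likely than 2.5%.

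Both confirmatory conclusions rest on that error rate. The plan chooses a per-protocol primary analysis in order to avoid bias towards non-inferiority, so an uncorrected source of false non-inferiority runs against its own aim. Because the sensitivity analysis reuses the same model, no analysis described would show whether the conclusions depend on independence.

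**Working it through.** **Inputs from the documents.** 60 per arm, 10% missing (54 analysed per arm), margin 4, two-sided 95% interval with one bound used, pre-treatment SD 3.78, post-treatment SD 4.07 (CBT arm), groups of 3 to 6.

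**Assumptions, because the documents give no figure.** Group ICC (as a share of baseline-adjusted variance) 0 to 0.20; CBT-therapist ICC 0.05; 6, 10 or 15 CBT therapists; pre-post correlation 0.4, with other values as checks. The difference is taken as B4DT minus CBT, so that higher means B4DT is worse.

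**Step 1: the plan's own figures under independence.** SE = 4.07 × √(2/54) = 0.783. Power = Φ(4/0.783 − 1.96) = Φ(3.15) = 99.9%, which meets the stated bound. Under independence the ANCOVA is exact, so the 2.5% claim also holds there.

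**Step 2: error with clustering in B4DT groups.** The design effect in the B4DT arm is DE = 1 + (m − 1) × ICC, where m is group size. The ratio of true to reported SE is r = √((DE + 1)/2), and the actual one-sided error is 1 − Φ(1.96/r). For example, with m = 4.5 and ICC 0.10: DE = 1.35, r = √1.175 = 1.084, error = 1 − Φ(1.808) = 3.5%.

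| Assumed group ICC | Groups of 3 | Mean size 4.5 | Groups of 6 |
|---|---|---|---|
| 0.05 | 2.8% | 3.0% | 3.2% |
| 0.10 | 3.1% | 3.5% | 4.0% |
| 0.20 | 3.7% | 4.6% | 5.5% |

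At ICC 0.01 and m = 4.5 the error is 2.6%. At ICC −0.05 the test is conservative (1.8% to 2.2% over these sizes).

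**Step 3: simulation of the planned ANCOVA and of the proposed interval.** The true difference is 4, with mixed groups of 3 to 6 and 100,000 trials per row (Monte Carlo error 0.05 to 0.07 points). CR2 is the small-sample-corrected cluster-robust variance with Satterthwaite degrees of freedom, clustered by therapy group.

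| Assumed group ICC | ANCOVA error | CR2 error | CR2 mean half-width |
|---|---|---|---|
| 0 | 2.62% (exact value 2.5%) | 2.59% | 1.45 |
| 0.05 | 2.99% | 2.55% | 1.51 |
| 0.10 | 3.56% | 2.59% | 1.57 |
| 0.20 | 4.45% | 2.65% | 1.67 |

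The ANCOVA half-width is 1.43. At ICC 0.10 its reported SE is 0.72 against a true SE of 0.78. For the superiority test at a true difference of 0, ANCOVA error is 3.1%, 3.7% and 4.4% at ICC 0.05, 0.10 and 0.20. Pre-post correlations of 0, 0.2 and 0.6 give 3.0-3.1%, 3.4-3.7% and 4.4-4.7%. With the B4DT residual SD at 0.75 to 1.25 times the CBT value, CR2 error is 2.4-2.7%; at 1.5 times it is 2.7-2.9%.

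**Step 4: CBT-therapist clustering at an assumed ICC of 0.05, over group ICC 0 to 0.20.**

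| CBT therapists | ANCOVA | CR2, group only | CR2, group and CBT therapist |
|---|---|---|---|
| 6 | 3.5-5.6% | 3.4-3.7% | 2.3-2.6% |
| 10 | 3.1-5.0% | 2.9-3.1% | 2.3-2.6% |
| 15 | 2.9-4.9% | 2.9-3.0% | 2.3-2.6% |

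**Step 5: when the verdict would change.** At ICC 0.10 the ANCOVA typically accepts estimates below 4 − 1.43 = 2.57, and CR2 those below 4 − 1.57 = 2.43. Only an estimate between about 2.43 and 2.57 would be judged differently.

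**Step 6: power.** At the planning SD and group ICC 0.20, power with the group CR2 interval is 99.6% (correlation 0.4) or 99.0% (correlation 0). The stated bound survives.

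**The case against.** The strongest case on the other side has five parts.

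- **The 2.5% sentence may only address multiplicity.** It can be read as saying that testing non-inferiority and then superiority does not inflate error, with the model's assumptions taken for granted. That is a fair reading of intent, but the interval is still too narrow under net positive clustering, and the plan neither states nor defends independence.
- **The ICC is unknown and may be small.** One therapist per patient and individually tailored exposure could keep it low, and at zero or below the claim holds. Correlations can also offset: group ICC 0.05 (mean size 4.5) with CBT-therapist ICC −0.02 (caseload 10) gives 2.49%. This stands, and it is why only a conditional conclusion is drawn. The group format and shared leader remain, and the documents give no basis for assuming zero.
- **The practical effect is small.** With group ICC 0.10 and no true difference, ANCOVA and CR2 disagreed on non-inferiority in about 0.1% of 3,000 simulated trials. This stands.
- **The proposed confirmatory interval leaves CBT therapists uncorrected.** With 6 therapists at ICC 0.05 its error is 3.4-3.7%, above the 3.0% that the plain ANCOVA shows at group ICC 0.05 alone. This also stands. The reworded claim has to say so, and a sensitivity analysis has to cover it.
- **Parts of the remedy are untested.** The mixed model was not re-run, and clustering by group leader and B4DT therapists shared across groups were not simulated. The identifiers may already be recorded, and the unseen code may already handle clustering. If it does, the text needs to match it.

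**Conclusion.** The point holds. As described, the primary ANCOVA, its intention-to-treat refit and the power simulation ignore clustering, although one arm is treated in groups. The unconditional 2.5% statement fails if correlation within groups or therapists is net positive, and it fails in favour of B4DT. With mixed group sizes and group clustering alone, the error is about 3.0%, 3.6% and 4.5% at assumed ICCs of 0.05, 0.10 and 0.20. CBT-therapist clustering, if present, adds to this.

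The inflation is modest and is trivial near ICC 0. The power claim is not affected at the planning SD. The ICCs, therapist numbers and pre-post correlation are assumptions; that the text contains no clustering term is not. The correction is cheap, and the error rate it protects supports both confirmatory conclusions, so it should be made.

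**What to change.** 1. Record three identifiers, if they are not already collected: therapy group, group leader and therapist.
2. Keep the ANCOVA point estimate (arm and baseline Y-BOCS). Base the confirmatory 95% interval, for non-inferiority, superiority and the intention-to-treat refit, on a CR2 variance with Satterthwaite degrees of freedom. The cluster is the therapy group in B4DT. Each CBT patient, and each B4DT patient who never joins a group, is a separate cluster.
3. Pre-specify three sensitivity analyses: a partially nested mixed model with a random intercept for therapy group in B4DT only; CR2 with CBT therapist added as a cluster; and CR2 clustered by B4DT group leader. Report the ICC with its interval.
4. Reword the 2.5% statement. It allows for correlation within therapy groups. It is conditional on no remaining clustering by CBT therapist, or by B4DT leaders or therapists shared across groups, which the confirmatory interval does not correct.

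**Cost.** SAP wording, a short code edit and three data fields. Design and sample size do not change. At pre-post correlation 0 the mean half-width is 1.65, 1.71 and 1.82 at ICC 0.05, 0.10 and 0.20, against 1.56 for the ANCOVA. Adding CBT therapist as a cluster with 6 therapists gives a half-width of 1.66-1.88, and power at group ICC 0.20 of 98.5% (correlation 0.4) or 96.5% (correlation 0), still above the stated 95%.

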Obsessive-compulsive disorder (OCD) is a disabling psychiatric disorder characterized by recurrent uncontrollable and unwanted thoughts (obsessions), and repetitive behaviors in response to those obsessions (compulsions). The lifetime prevalence of OCD is 2-3% [1], and the time-consuming symptoms often interfere with all aspects of daily life. Moreover, population-based studies have shown that OCD is associated with academic underachievement across the lifespan [2] and with substantial labor market marginalization, including higher risk of receiving disability pension, being on long-term sickness absence, and long-term unemployment [3].

One of the recommended first-line treatments for OCD is individual cognitive behavioral therapy (CBT) that includes exposure and response prevention (ERP). In CBT, patients are exposed to situations that trigger obsessions while actively refraining from performing compulsions. Although it is an effective treatment with 65% of participants responding to treatment [4], CBT typically requires weekly sessions during at least 3 months [5]. This extensive time-frame requires significant effort and persistence from patients and increases the risk of dropout. Moreover, a substantial proportion of patients remain impaired even among those who complete the treatment.

In response to this, several condensed formats of CBT have been developed in various countries. Amongst them is the Bergen 4-Day Treatment (B4DT), developed in Norway. In this treatment, patients receive intensive CBT at the clinic for 4 consecutive days. B4DT has been shown to achieve response rates over 90% when delivered in regular care in several uncontrolled treatment trials, and one randomized controlled trial (RCT) that used waitlist and self-help as controls [6]. However, it has yet to be compared to the gold standard CBT.

In this non-inferiority RCT, we will test the efficacy of B4DT compared to gold standard CBT. If B4DT turns out to be non-inferior to traditional CBT, the range of evidence-based options will be broadened and patients may be able to achieve clinically meaningful improvements within a shorter period of time.

Research questions

The overall approach of this study is to directly compare the intensive Bergen 4-day treatment (B4DT) to gold-standard individual cognitive behavior therapy (CBT) for adults with OCD.

Primary outcome

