The primary outcome is OCD severity as assessed by the blind rater-administered Yale-Brown Obsessive-Compulsive Scale (Y-BOCS). Specifically, we will test whether B4DT is non-inferior to

standard CBT 14 weeks after treatment start. The non inferiority margin is set to 4 points on the Y-BOCS.

Non-inferiority designs test whether a novel treatment is not unacceptably less efficacious (in this case, 4 points) than another treatment whose efficacy has already been established. However, a non-inferiority study may also be used to test for superiority without inflating the false-positive rate [7]. We will therefore sequentially test 1) whether B4DT is non-inferior to gold standard CBT , and 2) whether B4DT is superior to gold standard CBT.

Secondary outcomes

Our secondary objectives are to compare B4DT and gold standard CBT with regards to:

- 1) Time to response. We hypothesize that B4DT, due to its intensive design, will provide a faster response than gold- standard CBT. A comparison of the proportion of treatment responders at week 4 and week 7 will be used to test this hypothesis.
- 2) Rates of response and remission. The proportion of participants in response and remission will be compared 14 weeks after treatment start. For these outcomes, we have no directed hypotheses.
- 3) Dropout rate. We will test whether the proportion of patients that discontinue treatment prematurely (i.e., complete less than 50% of the treatment) differs between the B4DT and the gold standard CBT arm. For this outcome, we have no directed hypothesis.
- 4) Cost-effectiveness. Health economic data will be collected using clinic data on therapist usage and the Treatment Inventory of Costs in Psychiatric Patients [11]. Between-group costs will be calculated and compared 14 weeks after treatment start. The emphasis will be on cost-effectiveness analyses using responder status as outcome and health-care provider as the cost perspective. For this outcome, we have no directed hypothesis.
- 5) Negative effects. The total score of the Negative Effects Questionnaire will be compared 14 weeks after treatment start, as well as the prevalence of severe adverse events. For this outcome, we do not have a directed hypothesis.

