To explore whether B4DT leads to a faster treatment response than individual CBT, the proportion of responders in the two treatments will be compared 4 weeks after treatment start. The 95% confidence intervals of the odds ratio of response will be calculated for this purpose. Because the B4DT-group will have received their full treatment dose at the point of assessment while the gold standard CBT-group will have received only about 25%, there are strong reasons to believe that, from this perspective, B4DT will lead to faster symptom relief. An identical analysis will be conducted at 7 weeks to evaluate whether there is a difference between the treatments when participants in the individual CBT group have received 50% of the treatment.

Rates of response and remission

The proportion of participants in response and remission will be compared 14 weeks after treatment start. Response is defined as a reduction of 35% or more on the Y-BOCS and a CGI-I score of 1 or 2. Remission is defined as a Y-BOCS score of 12 or less and a CGI-S score of 1 or 2. Proportions will be compared using a two-sided two-proportions z-test.

Dropout rate

To explore whether the groups differ in terms of treatment completion, we will compare whether the proportion of patients that discontinue treatment prematurely differs between B4DT and gold standard CBT. A dropout will be defined as a patient in the B4DT arm that participates in less than 1.5 full days at the clinic, or a patient in the gold standard CBT arm that participates in less than 8 CBT sessions. Proportions will be compared using a two-sided two-proportions z-test.

Negative effects

To describe negative treatment effects, a two-sample t-test will be used to compare the total NEQ-scores at the primary endpoint (scores on the subscales will be presented in the supplement). The additional semi-structured questions about suicidal behaviors and thoughts, hospitalization, deterioration of psychiatric symptoms, and psychiatric care outside the study, will be reported in a frequency table.

Cost effectiveness

Health economic data will be collected using the self-rated Treatment Inventory of Costs in Psychiatric Patients (TIC-P) questionnaire [11]. The TIC-P records costs for the past month

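### Is the B4DT completion cut-off of 1.5 days really half of a four-day course?

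*Combined protocol and SAP*

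**What the plan says.** Under Statistical analysis, Primary outcome, Y-BOCS, the primary ANCOVA is per protocol. It takes participants who received at least 50% of treatment, made concrete as having "attended at least 8 sessions of individual CBT or 1.5 days of B4DT", and who also completed the 14-week assessment. The list of secondary outcomes under Research questions defines dropouts as patients who "complete less than 50% of the treatment". The later Dropout rate section makes this fewer than 8 CBT sessions or, for B4DT, a patient who "participates in less than 1.5 full days at the clinic".

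On course length, the Individual CBT section says "Patients will receive 16 90-minute sessions of individual CBT for OCD". The Introduction says of B4DT that "patients receive intensive CBT at the clinic for 4 consecutive days". The B4DT section describes day 1 as psychoeducation and choice of exposure tasks, days 2 and 3 as therapist-assisted exposure, "up to 7 hours of ERP per day", and day 4 as summary, relapse prevention and planning. It gives no length for days 1 and 4.

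For sensitivity, "the same ANCOVA model will be used again but with an intention to treat approach".

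**The concern.** One percentage is applied to both arms, but on a plain count of days it matches only the CBT cut-off. A B4DT patient who stops after 1.5 of four equal days has had 37.5% of the course and stays in the primary analysis. A CBT patient with 6 or 7 of 16 sessions (37.5% or 43.8%) is removed from it and counted as a dropout.

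The plan makes the per-protocol analysis primary to guard against bias towards non-inferiority, so a completion rule that is looser in the experimental arm would be unwelcome. It could also flatter B4DT in the dropout comparison. And an unstated denominator could, in principle, be settled after outcomes are known.

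**Working it through.** **The plan's own figure.** CBT: 8/16 = 50%. In hours, 8 × 1.5 = 12 of 16 × 1.5 = 24, again 50%. Guided exposure runs through sessions 3 to 14, so the first 8 sessions contain 6 of 12 exposure sessions, also 50%. The CBT half reproduces.

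**B4DT.** Let days 2 and 3 each count as 1 full day, and let days 1 and 4 each count as *d* of a full day. The document does not give *d*, so the values below are assumptions.

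- Course length = 2 + 2*d*
- Share of course at the cut-off = 1.5 / (2 + 2*d*)
- CBT equivalent = share × 16 sessions
- Share of the two exposure days, if attended in order = (1.5 − *d*) / 2

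| *d* (assumed) | Course, full days | Share at 1.5 days | CBT equivalent | Share of exposure days |
|---|---|---|---|---|
| 1 | 4.0 | 37.5% | 6.0 | 25% |
| 0.75 | 3.5 | 42.9% | 6.9 | 37.5% |
| 0.5 | 3.0 | 50% | 8.0 | 50% |
| 0.25 | 2.5 | 60% | 9.6 | 62.5% |

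The B4DT rule can be looser than, equal to or stricter than the CBT rule. At *d* = 0.5 both the course share and the exposure share match CBT, and 1.5 full days is exactly day 1 plus day 2.

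**Effect on the primary outcome.** Inputs from the Sample size calculation: a pre-treatment mean of 22.6, "a post-treatment mean of 12.9 (SD = 4.07) for the gold standard CBT arm", no true difference, and 60 per arm with 10% missing, so 60 × 0.9 = 54 analysed. Suppose *k* of those 54 are retained B4DT patients in the disputed band.

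- No improvement: each lies 22.6 − 12.9 = 9.7 points above the mean. Shift = *k* × 9.7/54 = 0.18, 0.36 and 0.54 points for *k* = 1, 2 and 3. The first is 0.18/4 = 4.5% of the margin. This raises the B4DT mean and works against non-inferiority.
- Extreme early improver with a score of 0: shift = 12.9/54 = 0.24 points per patient, about 6% of the margin, in favour of non-inferiority.

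**Effect on dropout.** Each reclassified patient moves an arm's rate by 1/60 = 1.7 percentage points; three move it by 5.0. With a two-proportion z-test and an assumed 3/60 in one arm, 4, 5 or 6 of 60 in the other gives p = 0.70, 0.46 or 0.30. Even 0/60 against 3/60 gives p = 0.08.

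**The case for a change.** The strongest case for acting is that the denominator cannot be derived from the text. The primary-analysis section speaks of days and the Dropout rate section of full days. Take a patient who attends day 1 and half of day 2. Counted in programme days, that is 1.5 and the patient is a completer. Counted in full days with day 1 as a half-day, it is 1.0 and the patient is a dropout. Read carelessly, one person could be both. A plan that stresses pre-specification should not leave that open, and a sentence would close it.

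What stands is that the lengths of days 1 and 4 are missing and that the 50% cannot be verified for B4DT.

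The rest is weaker. The two definitions are complements (at least 1.5 against less than 1.5), so an analyst will build both from one attendance variable, and the more specific full-day wording narrows the shorter one without contradicting it. The 37.5% depends on equal days, an assumption the document does not make and which its description of days 1 and 4 does not suggest. Replacing the rule with 2 of 4 scheduled days is not shown to be better: if days 1 and 4 are half-days, it is the same rule for anyone who attends in order.

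**Conclusion.** This is a gap that analysts can fill sensibly, not an arithmetic error, and no change to the plan is needed. The cut-offs of 8 sessions and 1.5 days are numerically the same in the primary-analysis and dropout definitions. The half-day reading of days 1 and 4 explains why the figure is 1.5 and gives parity with CBT. That reading is an inference; across the assumed day lengths the share runs from 37.5% to 60%, so no consistent advantage to B4DT is shown.

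The stakes are small. The rule matters only for patients who stop in a narrow band of a four-day course and, for the primary analysis, still complete the 14-week assessment. The document does not say how many to expect. At one to three such patients (assumed), non-improvers shift the B4DT mean by 0.18 to 0.54 points against a 4-point margin, in the conservative direction; early improvers would shift it the other way, so the net direction is unknown. The pre-specified intention-to-treat rerun of the same ANCOVA is untouched by the cut-off, and dropout carries no directed hypothesis and is declared exploratory. Recording how days 1 and 4 are credited would be tidy documentation, but it would alter neither the design nor any planned analysis.
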